4.5 Concomitant Medications/Treatments

4.5.1 Permitted Medications

All treatments that the investigator considers necessary for a subject's welfare may be administered at the discretion of the investigator in keeping with the community standards of medical care. All concomitant medication will be recorded on the case report form (CRF) including all prescription, over-the-counter (OTC), herbal supplements, and IV medications and fluids. If changes occur during the trial period, documentation of drug dosage, frequency, route, and date may also be included on the CRF.

Subjects are permitted the use of topical, ocular, intra-articular, intranasal, and inhalational corticosteroids (with minimal systemic absorption). A brief (less than 3 weeks) course of corticosteroids for prophylaxis (eg, contrast dye allergy) or for treatment of non-autoimmune conditions (eg, delayed-type hypersensitivity reaction caused by a contact allergen) is permitted. Inhaled or topical steroids, and adrenal replacement steroids are permitted at any dose in the absence of active autoimmune disease.

NU Study Number: NU 16L04
Other Study Number: CA 209-801

Concomitant palliative and supportive care for disease related symptoms (including bisphosphonates and RANK-L inhibitors) is allowed if initiated prior to first dose of study therapy.

All concomitant medications received from informed consent until 30 days after the last dose of trial treatment should be recorded. Concomitant medications administered past 30 days of treatment should be recorded if associated with an SAE.

4.5.2 Prohibited Medications

Subjects are prohibited from receiving the following therapies during the Screening and Treatment Phase of this trial:

- Anti-cancer systemic chemotherapy or biological therapy (≤ 14 days prior to registration)
- Immunotherapy not specified in this protocol (≤ 14 days prior to registration)
- Investigational agents (≤ 14 days prior to registration)
- Corticosteroids are not permitted ≤ 14 days prior to registration unless they fall under the criteria listed in 4.5.1
- For the purpose of imaging with CT scan with IV contrast, metformin can be held according to the institution's CT scan protocol.

4.6 Duration of Therapy

Patients may continue with treatment until any of the following occur:

- Disease progression, unless the patient meets criteria for continuing treatment beyond progression. See section 4.4 for details.
- Development of an inter-current illness that prevents further administration of treatment
- Unacceptable adverse event(s) requiring discontinuation of at least one study drug
- Patient decides to withdraw from either study treatment or the as a whole study
- The treating investigator determines that the patient should be taken off treatment for any reason (i.e. changes in condition, inability to comply with study treatment or procedures)

4.7 Duration of Follow Up

All patients will be followed for adverse events for 30 days after last dose of study treatment (100 days for SAEs), or until the patient starts a new treatment, whichever occurs first. Patients who discontinue treatment for unacceptable adverse event(s) will be followed until resolution or stabilization of the adverse event (i.e. the grade is not changing). If a patient stops treatment due to unacceptable adverse event(s) but has not demonstrated disease progression, then the patient will be followed with imaging studies every 8 weeks until the time of progression radiographically according to RECIST 1.1 criteria. In the event that a radiographic response is detected, then this event will be included as a response in the final analysis, and the time of progression used in calculation of the survival analysis. Patients will be followed for survival status every 3 months for 1 year and every 6 months for a total of 3 years after treatment discontinuation for survival or progression of disease.

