4.3.4 Metformin

The most common adverse reactions to metformin are diarrhea, nausea/vomiting, flatulence, indigestion, and headaches. These side effects occur most commonly upon initiation of therapy and are short lived. These effects are mitigated by dose escalation regimens that are used in this trial. Dose reduction or discontinuation will be applied in patients with persistent gastrointestinal symptoms related to metformin. A rare but serious side effect of metformin is lactic acidosis, which is most common in patients with renal insufficiency and congestive heart failure. Lactic acidosis can be evaluated by checking a patient's renal function in addition to their serum lactic levels. Any clinical or laboratory indication of metabolic acidosis will lead to immediate discontinuation of metformin.

For commonly observed gastrointestinal AEs of metformin such as nausea, vomiting and diarrhea the dose should be withheld. Metformin should be held until the AE resolves to \leq Grade 1 or baseline and restarted at a lower dose level as per Table 4-3. Metformin can be held for a maximum of 28 days. Patients who permanently discontinue metformin for toxicity must come off study treatment – they may not receive nivolumab monotherapy on-study.

Metformin-induced side effects as determined by the study investigator should be managed as listed below in tables 4-3 and 4-4.

Table 4-3: Metformin-related toxicity dose reductions	
CTCAE Grade	Metformin Dosing
0-2	No change from original starting dose
3 (1 st occurrence)	Hold until resolved to \leq grade 1 or baseline, then reduce to lower dose
3 (2 nd occurrence)	Hold until resolved to \leq grade 1 or baseline, then reduce to lower dose
3 (3 rd occurrence) or 4	Discontinue treatment

Table 4-4: Dose reduction of Metformin for toxicity	
Current dose	Reduced dose
2000 mg	1500 mg
1500 mg	1000 mg
1000 mg	500 mg
500 mg	Discontinue*

Note: For the purpose of imaging with CT scan with IV contrast, metformin can be held according to the institution's CT scan protocol.

*Patients will discontinue all study treatment

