4.8 Removal of Subjects from Study Treatment and/or Study as a Whole

Patients can be taken off the study treatment and/or study as a whole at any time at their own request, or they may be withdrawn at the discretion of the investigator for safety, behavioral or administrative reasons. The reason(s) for discontinuation must be clearly documented on the appropriate eCRF and may include:

- Patient voluntarily withdraws from treatment (follow-up permitted)

NU Study Number: NU 16L04
Other Study Number: CA 209-801

- Patient withdraws consent (no follow-up permitted)
- Patient is unable to comply with protocol requirements
- Patient demonstrates disease progression
- Patient experiences unacceptable toxicity
- Treating physician determines that continuation on the study would not be in the patient's best interest
- Patient becomes pregnant
- Patient develops a second malignancy that requires treatment which would interfere with this study
- Patient becomes lost to follow-up (LTf)

Patients who are permanently discontinued from receiving investigational product will be followed for disease progression and safety, including the collection of any protocol-specified blood specimens, unless consent is withdrawn or the subject is lost to follow-up or administered subsequent therapy. All subjects will be followed for survival and disease progression. Subjects who decline to return to the site for evaluations will be offered follow-up by phone every 3 months as an alternative.

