8. The same modality used at baseline should be used throughout for imaging. CT imaging with contrast will occur every 2 cycles starting with Cycle 3 Day 1 (\pm 7 days) and should include chest, abdomen, and pelvis. Neck will be included only if measurable lesions are present. Metformin should be held prior to scans per each institutional protocol. Tumor measurements will be performed using RECIST 1.1. Progressive Disease (PD) must be confirmed by repeat scan within 8 weeks at least after 4 weeks. Patients with a known history of CNS disease must have CNS imaging at screening to rule out activity.
9. Patients will undergo a fresh tissue biopsy prior to study enrollment, unless deemed to be clinically inappropriate per PI. If not feasible, archived tissue will be used (if available).
10. The maximum time interval between registration and the first dose of study drug will be 14 days
11. Nivolumab will be given as follows:
Cycle 1-4: 240mg IV over 30 minutes (-5 / +15 minutes) every 14 days (Day 1 & 15, \pm 3 days)
Cycle 5+: 480mg IV over 60 minutes (-10 / +15 minutes) every 28 days (Day 1, \pm 3 days) until disease progression, intolerance, or withdrawal of consent.
12. Metformin will be dispensed Day 1 of each cycle. Dosing will begin at 1,000mg po once daily and escalate by 500mg every 7 days until the final dose of 2,000mg is reached. Patients will return unused drug and drug bottles at each study visit and will maintain a drug diary to track compliance.
13. The end of treatment visit should occur 30 days after the last dose of study treatment (+/- 7 days) or before starting another line of treatment, whichever comes first.
14. Correlatives from peripheral blood will be collected for all patients at Induction Day 1, C1D1, C3D1, and at the EOT. Biopsy samples (fresh or archived) will be collected for all patients if possible. See separate lab manual for specifications. See section 9.0 for details.
15. Metformin monotherapy will be given at 1,000mg PO QD during the 7-day Induction period, prior to starting nivolumab on Cycle 1 Day 1.
16. After patients come off treatment they will be followed up at 3, 6, 9, and 12 months (\pm 7 days) and then every 6 months (\pm 14 days) for 3 years for survival and progression of disease via either clinic visits or phone calls.

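### Section 4.7 counts responses found after a toxicity stop with no cut-off at new anti-cancer treatment, while 4.8 and possibly 6.3 point the other way, so another therapy's response could be credited to the combination

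*Combined protocol and SAP*

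**What the plan says.** Section 4.7 deals with patients who stop for unacceptable adverse events without progression. They are "followed with imaging studies every 8 weeks until the time of progression radiographically according to RECIST 1.1 criteria". The scoring rule follows: "In the event that a radiographic response is detected, then this event will be included as a response in the final analysis". The paragraph does use a cut-off at new treatment, "or until the patient starts a new treatment, whichever occurs first", but attaches it to adverse-event follow-up only.

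Other sections bear on the same patients:

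- **4.8** follows patients who are permanently off investigational product for progression and safety "unless consent is withdrawn or the subject is lost to follow-up or administered subsequent therapy". The next sentence has no such exception: "All subjects will be followed for survival and disease progression".
- **Table 5-1, footnote 16** has patients followed after treatment "for survival and progression of disease via either clinic visits or phone calls".
- **10.3** takes the best response before progression, with no mention of new therapy, and runs the primary analysis on the evaluable set.
- **6.3** treats every treated patient as evaluable except those taken off the study for adverse drug reactions.
- **10.1** measures the primary endpoint, ORR, at 24 weeks from the start of treatment.
- **4.5.2** limits other therapy only while on study: "Subjects are prohibited from receiving the following therapies during the Screening and Treatment Phase of this trial".
- **4.3.4** takes a patient who permanently stops metformin for toxicity off all study treatment: "they may not receive nivolumab monotherapy on-study".

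**The concern.** Sections 4.7 and 10.3, read on their own, leave the response window open after the patient has moved to another therapy. A response to that therapy carries no information about nivolumab plus metformin.

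The case is possible under the plan. A PD-1-naive patient who cannot tolerate metformin must leave study treatment. Section 1.4 says nivolumab is approved for this disease, so that patient may receive it alone off study. Section 1.3.2 uses single-agent nivolumab as the historical control for Group A. Under 4.7, a response to the control regimen could then be counted for the combination.

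ORR is the primary endpoint and the boundaries are low: 3 of 24 in one design and 8 of 25 in the other. A single misattributed response can decide an arm.

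**Working it through.** The designs are named by size (9/24 and 12/25) because 1.3.2 and 10.2 assign them to opposite arms.

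**Step 1. Reproduce the plan's figures (10.2).** Let b(x; n, p) be the binomial probability, n1 and n the stage 1 and total sizes, and r1 and r the largest counts that stop or fail the arm.

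- P(stop early) = Σ b(x; n1, p0) for x ≤ r1
- Type I error = Σ b(x; n1, p0) · P[Bin(n − n1, p0) ≥ r + 1 − x] for x > r1

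| Design | n1, r1, n, r | p0 | P(stop early) | Type I |
|---|---|---|---|---|
| 9/24 | 9, 0, 24, 2 | 0.05 | 0.95^9 = 0.630 | 0.0931 |
| 12/25 | 12, 2, 25, 7 | 0.20 | 0.558 | 0.0991 |

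These agree with the stated 63%, 56% and 10% limit. The 56% holds at a true rate of 20%, although 10.2 prints 5%.

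**Step 2. How often is a null arm one response short?** P = Σ b(x; n1, p0) · b(r − x; n − n1, p0) for x > r1.

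- 9/24: 0.2985 × 0.3658 + 0.0629 × 0.4633 = 0.138. Among arms reaching stage 2: 0.138 / 0.370 = 37.4%.
- 12/25: the same sum over x = 3 to 7 gives 0.086. Among arms reaching stage 2: 0.086 / 0.442 = 19.5%.

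In those arms one extra counted response turns failure into success.

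**Step 3. Type I error if late responses count.** Let d be the share of all patients who stop for toxicity without progression or response, start another therapy and are still scanned. Let g be the response rate to that therapy, and q = d × g. Each patient is then an on-treatment responder (p0), a late responder (q) or neither (1 − p0 − q). As 4.7 speaks of the final analysis, stage 1 uses on-treatment responders only and the final count adds late responders among all n. The on-treatment rate stays at the null.

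The documents give no value for d, so it is assumed. For g, Section 1.4.2 gives 9% for docetaxel.

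| d | q at g = 9% | 9/24 | 12/25 |
|---|---|---|---|
| 0 | 0 | 9.3% | 9.9% |
| 1% | 0.0009 | 9.6% | 10.1% |
| 2% | 0.0018 | 9.9% | 10.3% |
| 5% | 0.0045 | 10.8% | 10.8% |
| 10% | 0.0090 | 12.2% | 11.7% |

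No 24-week limit is modelled. If 10.1 is enforced, fewer late responses qualify and the increases shrink.

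**The case against.** The strongest reply is that 4.7 and 4.8 can be read together: 4.7 sets the scan interval and 4.8 says when scanning ends. On that reading no scans follow new therapy and nothing is misattributed. The two passages that seem to extend follow-up to everyone do not clearly undo this. Footnote 16 permits phone contact, 4.8 offers it too, and neither schedules scans. This part stands. A reader might infer from 4.7 that responses to other therapies *will* be scored for the combination, but the documents support only that they *could* be. What remains is that 4.8 does not say which scans count for ORR, whereas 4.7 does state a counting rule, without a limit.

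Section 6.3 is a second obstacle. If being taken off the study for an adverse drug reaction includes stopping study drug for toxicity, these patients are in neither numerator nor denominator and no inflation arises. But 4.7 then contradicts 6.3, since it counts responses in patients whom 6.3 excludes. The rule needs repair on either reading.

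Third, the chain of events is long: a toxicity stop without progression or response, new therapy before progression, and a response, all by week 24 if 10.1 holds. Metformin normally steps down to 500 mg before it is abandoned (4.3.4). Section 1.4.2 reports 7% grade 3-4 treatment-related events on nivolumab in squamous disease, a benchmark rather than a stopping rate. Nothing in the plan shows that new therapy before progression is expected, only that it is allowed. Small values of d are therefore the more plausible ones, and at 1% to 2% type I error is close to nominal.

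Larger figures are tempting. With d = 20% and g = 20% (nivolumab alone, 1.4.2) the 9/24 design reaches 21.3%. That figure should not be used: 1.3.2 gives the 5%-null design to PD-1-pretreated patients, for whom 10.3 puts the response rate of refractory patients at 5%. At g = 5% the same design gives 10.1%, 10.9% and 12.5% for d = 5%, 10% and 20%. If the arm labels in 10.2 are used instead, nivolumab alone at 20% already passes that design about 80% of the time (exact power 0.805), and the arm assignment is the larger problem.

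**Conclusion.** The concern holds in limited form. Sections 4.7 and 10.3 set a response window for the primary endpoint that does not close at new anti-cancer treatment, 4.8 conflicts with 4.7, and 6.3 may conflict as well. A response to another therapy could be credited to the combination if 4.7 is the section followed.

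The average effect is probably small: type I error of about 9.6% to 12.2% (9/24) and 10.1% to 11.7% (12/25), for an assumed d of 1% to 10% and a 9% response rate to later therapy. There is no effect if 4.8 stops the scans, and less if the 24-week time point is enforced. The practical reason to act is the low boundary. Under the null, 13.8% of 9/24 arms and 8.6% of 12/25 arms end one response short, and there a single such case would reverse the conclusion.

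**What to change.** - **4.7:** count a radiographic response only if it is detected before any new anti-cancer treatment, meaning systemic therapy or radiotherapy to a target lesion.
- **10.3:** close the best-response window at the earlier of progression and new anti-cancer treatment.
- **6.3:** state that treated patients who stop for toxicity stay in the denominator. Without this change the rule in 4.7 and the evaluable set remain at odds.
- **4.8:** cross-refer to 4.7, so that both sections give the same end to response follow-up.
- **Sensitivity analysis:** report ORR with later responses counted, where such scans exist.

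Genuine delayed responses after study drug stops would still count until other treatment begins. The cost is a clause or sentence in each of four sections and one CRF field for the date and type of first new treatment. The date must be known in any case, since the adverse-event cut-off in 4.7 and the exception in 4.8 both depend on it. Sample size, boundaries and supportive-care policy do not change.

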4.8 Removal of Subjects from Study Treatment and/or Study as a Whole

Patients can be taken off the study treatment and/or study as a whole at any time at their own request, or they may be withdrawn at the discretion of the investigator for safety, behavioral or administrative reasons. The reason(s) for discontinuation must be clearly documented on the appropriate eCRF and may include:

- Patient voluntarily withdraws from treatment (follow-up permitted)

NU Study Number: NU 16L04
Other Study Number: CA 209-801

- Patient withdraws consent (no follow-up permitted)
- Patient is unable to comply with protocol requirements
- Patient demonstrates disease progression
- Patient experiences unacceptable toxicity
- Treating physician determines that continuation on the study would not be in the patient's best interest
- Patient becomes pregnant
- Patient develops a second malignancy that requires treatment which would interfere with this study
- Patient becomes lost to follow-up (LTf)

Patients who are permanently discontinued from receiving investigational product will be followed for disease progression and safety, including the collection of any protocol-specified blood specimens, unless consent is withdrawn or the subject is lost to follow-up or administered subsequent therapy. All subjects will be followed for survival and disease progression. Subjects who decline to return to the site for evaluations will be offered follow-up by phone every 3 months as an alternative.

4.9 Patient Replacement

If a patient is enrolled in the study but comes off study before cycle 1 day 1 of treatment, the patient may be replaced

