4.0 TREATMENT PLAN

4.1 Overview

Nivolumab and metformin combination will be administered intravenously and orally, respectively, until disease progression or intolerable toxicity. Metformin will be initiated during a 7-day Induction period at 1,000mg orally once daily. Metformin will then be escalated by 500mg every 7 days as tolerated (C1D1 and C1D8) until the full 2,000mg dose is reached. Extended release formulation - Glucophage XR will be used for the study and commercial supply will be used which will be purchased and dispensed by NU investigational pharmacy. During Cycle 1-4 (1 cycle = 28 days), nivolumab will be given at 240mg every 14 days (Day 1 & 15) over approximately 30 minutes (-5 / +15 minutes). Starting with Cycle 5 Day 1, nivolumab will be given at 480mg IV every 28 days over approximately 60 minutes (-10 / +15 minutes). Patients will be assessed for response every 8 weeks (2 cycles).

Note: Please refer to section 4.4 for patients who may continue treatment after initial progression.

Dosing schedule is summarized in the table below.

Table 4-1: Dosing of Nivolumab and Metformin

Drug	Dose	Route	Schedule
Nivolumab (Opdivo)	C1-4: 240mg C5+: 480mg	IV	Cycle 1-4: every 14 days Cycle 5+: every 28 days until progression of disease, intolerable toxicity, or withdrawal of consent
Metformin hydrochloride (Glucophage XR)	2,000mg*	PO	daily with evening meal until progression of disease, intolerable toxicity, or withdrawal of consent 
 • starting dose: 1,000mg • dose escalation plan: weekly by 500mg

*Metformin will be initiated at 1,000mg during the Induction period and escalate by 500mg (1 tablet) every 7 days until the final dose of 2,000mg.

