4.3 Toxicity Management & Dose Delays/Modifications

Any patient who receives at least one dose of study therapy will be evaluable for toxicity endpoints. Each patient will be assessed for the development of toxicity according to the timeframe referenced in the Schedule of Events table. Toxicity will be assessed according to the NCI CTCAE v. 4.03.

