6.3 Primary Endpoint

To assess anti-tumor activity of the combination treatment of nivolumab and metformin in patients with advanced non-small cell lung cancer: Anti-tumor activity will be assessed by objective response rate (ORR, complete response and partial response) using RECIST criteria. All patients who receive treatment will be considered evaluable except those removed from the study for adverse drug reactions.

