10.2 Sample Size and Accrual

Up to 49 patients (Arm A=24, Arm B=25) will be entered into the trial based on optimal Simon two stage design as below.

Arm A: In the first stage, 9 patients will be entered. If no patients show a response, then the trial will be terminated due to inactivity of the treatment. If 1 or more of 9 show a response, then an additional 15 patients will be added. If 2 or fewer of 24 show a response, then the trial will conclude that the response rate could be as low as 5%. If 3 or more respond, then the trial will conclude that the response rate is at least 20%. This design has a 20% chance of falsely concluding the rate is 5% (false negative Type II error rate = 20%, or power = 80%), and a 10% chance of falsely concluding that the rate is 20% (false positive Type I error rate = 10%). There is a 63% probability of early termination of the trial when the true response rate is 5%.

Arm B: In the first stage, 12 patients will be entered. If 2 or less patients show a response, then the trial will be terminated due to inactivity of the treatment. If 3 or more of 12 show a response, then an additional 13 patients will be added. If 7 or fewer of 25 show a response, then the trial will conclude that the response rate could be as low as 20%. If 8 or more respond, then the trial will conclude that the response rate is at least 40%. This design has a 20% chance of falsely concluding the rate is 20% (false negative Type II error rate = 20%, or power = 80%), and a 10% chance of falsely concluding that the rate is 40% (false positive Type I error rate = 10%). There is a 56% probability of early termination of the trial when the true response rate is 5%.

Due to inevaluable patients and dropout, target accrual will be 51 patients. It is anticipated that 2 patients will be accrued per month so that accrual to this study will take 2 years.

Thus, this study will be a single institution trial with duration of enrollment being 2 years. The study will be done via both internal and external referral system. Being one of the busiest lung cancer programs in the area with good advertisement plan towards partnering institutions on this clinical trial, the above accrual plan is deemed to be a feasible one.

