10.3 Data Analyses Plans

Summary of Analytic plan for primary objective	Summary of Analytic plan for secondary objectives

Please refer to the below sample size justification for the parallel Simon's two stage design which defines how the endpoints are met.
 
For Group A. Estimated ORR for historical control is 20% versus target ORR of 40% for nivolumab and metformin combination treatment.
	
Depth of response: waterfall plot Duration and persistence of response: swimmer's plot PFS: PFS at 1 and 2 years (Kaplan-Meier analysis) OS: OS at 1 and 2 years (Kaplan-Meier analysis) ORR, DCR by irRC (descriptive statistics,

NU Study Number: NU 16L04
Other Study Number: CA 209-801

For Group B. Estimated ORR for refractory patients is 5% versus target ORR of 40% for niovulomab and metformin combination treatment.
	
exact binomial confidence intervals) We will use descriptive statistics and graphical displays to evaluate change in serum biomarkers between pre- and post-treatment. A Wilcoxon signed rank test will be used to determine if there is a statistically significant change in serum biomarkers. Toxicities will be tabulated by type and grade.

--	---

The primary analysis will be on the evaluable analysis set, including all evaluable patients regardless of drug exposure. Clinical benefit rate will be defined as stable disease (for ≥ 12 weeks), complete or partial response by both the Response Evaluation Criteria in Solid Tumors (RECIST) and irRECIST. Maximum response prior to disease progression will be used. The overall response rate will be estimated by the proportion of overall response, and its 80% confidence interval (CI) and 95% CI will be estimated using the exact binomial distribution.

Additionally, we will evaluate overall response rate, defined as complete or partial response using RECIST guidelines in a similar manner. We will also perform similar analyses using Immune Related RECIST (irRECIST). Duration of response, defined as the duration from the first documentation of clinical benefit to the first documented progressive disease or death of any cause, whichever occurs first, will also be analyzed. For patients alive and progression-free at the time of data cut off, duration of response will be censored as of the last tumor assessment date. Duration of response will only be evaluated for the subgroup of patients with a clinical benefit using the Kaplan-Meier method.

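### Patients who take induction metformin and come off study before C1D1 are both replaceable (4.9) and, unless removed for an adverse drug reaction, evaluable (6.3, 10.3), and no rule says who counts toward 9/24 or 12/25

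*Combined protocol and SAP*

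**What the plan says.** Four places in the combined protocol and SAP bear on this.

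- Section 4.9 sets the replacement cut-off at C1D1: "If a patient is enrolled in the study but comes off study before cycle 1 day 1 of treatment, the patient may be replaced". It does not separate patients who have taken drug from those who have not, and replacement is optional.
- Drug starts earlier than that. Table 5-1, footnote 15: "Metformin monotherapy will be given at 1,000mg PO QD during the 7-day Induction period, prior to starting nivolumab on Cycle 1 Day 1". The treatment overview in 4.1 agrees: "Metformin will be initiated during a 7-day Induction period at 1,000mg orally once daily".
- Section 6.3 defines who is evaluable for ORR: "All patients who receive treatment will be considered evaluable except those removed from the study for adverse drug reactions".
- Section 10.3 applies that definition: "The primary analysis will be on the evaluable analysis set, including all evaluable patients regardless of drug exposure".

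For comparison, 4.3 sets the toxicity population by first dose: "Any patient who receives at least one dose of study therapy will be evaluable for toxicity endpoints".

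Section 10.2 ties the decisions to fixed counts: at least 1 of 9 and then 3 of 24 in one arm, at least 3 of 12 and then 8 of 25 in the other. It sets target accrual at 51 against a maximum of 49, to allow for inevaluable patients and dropout. Because 1.3.2 and 10.2 assign the response rates to opposite arms, I name the designs by their sizes.

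**The concern.** Someone who takes a few days of metformin and then comes off study before C1D1, for a reason other than an adverse drug reaction, meets both rules. Under 6.3 and 10.3 the patient belongs in the ORR denominator. Under 4.9 the patient may be replaced. The plan does not say which rule prevails, or whether the replacement fills the same slot or adds one.

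Such a patient will have no recorded response, because the first on-study scan is at Cycle 3 Day 1 (Table 5-1, footnote 8). Dropping and replacing the patient therefore removes a treated failure, on the basis of something that happened after treatment began. Section 4.9 asks for no reason and names no decision-maker, so the choice could differ from patient to patient. The trial is open-label and decides on small counts, so one or two patients can matter.

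**Working it through.** **1. Is induction metformin treatment?** Section 4.1 starts the regimen with it, 6.5.2 describes the week before C1D1 as metformin treatment, and Table 5-1 dispenses drug and collects adverse events in Induction. The natural reading is yes.

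**2. Who meets both rules?**

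| Leaves before C1D1 after taking metformin | 4.9 | 6.3 / 10.3 | Conflict |
|---|---|---|---|
| Removed for adverse drug reaction | replaceable | not evaluable | no |
| Off study for decline, withdrawal, loss to follow-up or death | replaceable | evaluable | yes |

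**3. Reproduce the stated designs (10.2).** With first-stage size n1, stop limit r1, total n and final limit r:

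P(positive) = sum over x > r1 of P(X1 = x) × P(X2 ≥ r + 1 − x), where X1 ~ Bin(n1, p) and X2 ~ Bin(n − n1, p).

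- 9/24 at p = 0.05: 0.2985 × 0.1710 + 0.0629 × 0.5367 + 0.0084 × 1 = 0.0931. Power at 0.20 is 0.8047. Early stop at 0.05 is 0.630.
- 12/25 at p = 0.20: 0.0991. Power at 0.40 is 0.8151. Early stop at 0.20 is 0.558.

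These match the stated 10% type I error, 80% power, and 63% and 56% early-stopping probabilities (the 56% at a true rate of 20%).

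**4. Leavers swapped out.** Let f be the share of metformin starters who leave before C1D1 in the conflicting group. The documents give no f, so it is assumed. The only related figure is the total allowance, 51 − 49 = 2 patients, or 2/51 = 3.9%, for all inevaluability and dropout. If the null rate p0 applies to everyone who starts metformin and leavers never respond, the rate among those counted is p0/(1 − f). For example, 0.20/0.98 = 0.2041.

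| f | 9/24 type I error | 12/25 type I error |
|---|---|---|
| 0 | 0.0931 | 0.0991 |
| 2% | 0.0975 | 0.1087 |
| 4% | 0.1021 | 0.1193 |
| 5% | 0.1045 | 0.1250 |

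If p0 instead describes only patients who reach nivolumab, swapping leavers out leaves 0.0931 and 0.0991 unchanged.

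**5. Leavers kept and also replaced.** The sizes grow while the cut-offs stay. One extra first-stage patient gives 10/25 with 0.1054 and 13/26 with 0.1219, if p0 applies to all treated. If leavers cannot respond and p0 describes those reaching C1D1, the error does not rise, but the rules are then applied to sizes the plan never specified.

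**6. Leavers counted and not replaced.** Sizes stay as stated. If the design rates describe patients reaching C1D1, the rate becomes p(1 − f):

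| f | 9/24 type I error / power | 12/25 type I error / power |
|---|---|---|
| 2% | 0.0889 / 0.7939 | 0.0902 / 0.7939 |
| 5% | 0.0828 / 0.7766 | 0.0778 / 0.7592 |

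**The case against.** The strongest defence is that the group is small and the trial concerns the combination. Section 4.9 speaks of coming off study, and 4.8 separates leaving treatment from leaving the study as a whole. A patient who stops metformin but stays in follow-up may not be replaceable at all. No scan is scheduled in the induction week, so scheduled imaging would not reveal progression then. The clear cases are withdrawal of consent, loss to follow-up or death within seven days. Evaluating a combination in patients who reach it is also a coherent phase II choice, and the 20% benchmark in 1.3.2 comes from single-agent nivolumab trials. All of this stands. It limits the size, but it does not tell the reader which rule governs the cases that remain.

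The cut-off wording in 4.9 could also be read as placing the start of treatment at C1D1, which would remove the conflict. The sections listed in step 1 point the other way, and no passage adopts that reading.

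Three stronger inferences should be resisted.

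- A reader might count metformin-intolerant leavers among those affected. Those removed for adverse drug reactions are already non-evaluable under 6.3, so 4.9 and 6.3 agree on them.
- A reader might conclude that following 6.3 must make the stages too large. That happens only if the patient is also replaced. Since 4.9 is permissive, counting without replacing satisfies both sections.
- A reader might take f = 10%, where the 12/25 error would be 0.1578. That means about 5 of 51 patients (0.10 × 51 = 5.1) coming off study within a week for reasons other than drug reactions, against an allowance of 2 of 51 for every cause.

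**Conclusion.** The conflict holds for a narrow group: patients who take induction metformin and come off study before C1D1 for a reason other than an adverse drug reaction. For them the primary denominator and the stage counts are undefined, and an optional rule allows treated failures to be exchanged.

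The numerical effect is probably small. At f = 2%, with leavers swapped out, only the 12/25 design passes the stated 10%. At 5%, which is already above the plan's whole dropout allowance, both do. These figures rest on an assumed f and on the null rate applying to everyone who starts metformin. Without the second assumption, swapping produces no inflation. The documents therefore do not show that the type I error is inflated. They show that the rule is unsettled in a trial decided by a few responses. It should be settled before any stage is assessed.

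**What to change.** - In 4.9, allow replacement only for patients who have taken no dose of either study drug.
- In 6.3 and 10.3, keep every patient who took metformin or nivolumab in the primary denominator and in the 9/24 and 12/25 counts, scored as a non-responder if no response is recorded. Say explicitly that this removes the adverse-reaction exclusion now in 6.3, which is a larger change than the replacement rule alone.
- Report ORR among patients with at least one nivolumab dose as a sensitivity analysis, and list every replaced patient with the reason.

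The change takes a few sentences and no new procedures. The cost is that ORR may be slightly lower. If the design rates describe patients who reach C1D1, power also falls as in step 6: to about 0.794 in both designs at f = 2%, and to 0.777 (9/24) and 0.759 (12/25) at f = 5%. The sponsor should accept that loss openly or re-size.
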